### Protocol Amendment Summary of Changes Table

Document History		
Document	Version Date	Summary and Rationale for Changes
Original protocol	13 January 2021	N/A

## 1. PROTOCOL SUMMARY

### 1.1. Synopsis

**Short Title:** 20-valent Pneumococcal Conjugate Vaccine Safety and Immunogenicity Study in Pneumococcal Vaccine–Naïve Adults 60 Years of Age and Older in Japan, Korea, and Taiwan

### Rationale

Pfizer is developing a 20vPnC candidate to expand protection against pneumococcal disease beyond that covered by current pneumococcal vaccines in children and adults. 20vPnC has the same composition as 13vPnC (Prevenar 13®) but contains an additional 7 pneumococcal conjugates to protect against serotypes responsible for a substantial burden of remaining pneumococcal disease. 20vPnC uses the same platform and contains the same excipients as 13vPnC. 20vPnC is in late-stage clinical development, and data from overseas Phase 3 studies in adults 18 years of age and older provide evidence that the safety profile is acceptable and similar to 13vPnC, and induces immune responses that are expected to support licensure for an adult ( $\geq 18$  years of age) indication in the United States, Europe, and other countries.

The purpose of this study is to assess the safety and immunogenicity of 20vPnC in adults  $\geq 60$  years of age in Japan, Korea, and Taiwan **CCI**

### Objectives, Estimands, and Endpoints

Objectives	Estimands	Endpoints
Primary Safety	Primary Safety	Primary Safety
To describe the safety profile of 20vPnC.	
In participants receiving at least 1 dose of study intervention and having safety follow-up after vaccination from each vaccine group:
 
 
• The percentage of participants reporting prompted local reactions within 10 days after the first vaccination (20vPnC or 13vPnC)
 
• The percentage of participants reporting prompted systemic events within 7 days after the first vaccination (20vPnC or 13vPnC)
 
• The percentage of participants reporting AEs within 1 month after vaccination with 20vPnC or 13vPnC
 
• The percentage of participants reporting SAEs within 1 month after vaccination with 20vPnC or 13vPnC
 
	
 
• Prompted local reactions (redness, swelling, and pain at the injection site)
 
• Prompted systemic events (fever, headache, fatigue, muscle pain, and joint pain)
 
• AEs
 
• SAEs
 

Primary Immunogenicity	Primary Immunogenicity	Primary Immunogenicity
To demonstrate that the immune responses to the 13 serotypes in 13vPnC (1, 3, 4, 5, 6A, 6B, 7F, 9V, 14, 18C, 19A, 19F, and 23F) induced by 20vPnC are noninferior to the immune response induced by 13vPnC.	In participants in compliance with the key protocol criteria (evaluable participants): 
 
For each of the 13 serotypes: GMR of serotype-specific OPA titers 1 month after 20vPnC to the serotype-specific OPA titers 1 month after 13vPnC
 
	
 
Serotype-specific OPA titers
 

To demonstrate that the immune responses to the 7 additional serotypes in 20vPnC (8, 10A, 11A, 12F, 15B, 22F, and 33F) induced by 20vPnC are noninferior to the immune response induced by PPSV23.	In evaluable participants: 
 
For each of the 7 additional serotypes: GMR of serotype-specific OPA titers 1 month after 20vPnC to the serotype-specific OPA titers 1 month after PPSV23
 
	
 
Serotype-specific OPA titers
 

Secondary Immunogenicity	Secondary Immunogenicity	Secondary Immunogenicity
To describe the immune responses to all 20 serotypes induced by 20vPnC.	In evaluable participants for each of the 20 serotypes: 
 
Serotype-specific OPA GMTs 1 month after vaccination* in each vaccine group
 
GMFRs in serotype-specific OPA titers from before to 1 month after vaccination* in each vaccine group
 
Percentage of participants with <math>\geq 4</math>-fold rise in serotype-specific OPA titers from before to 1 month after vaccination* in each vaccine group
 
Percentage of participants with serotype-specific OPA titers greater than or equal to the LLOQ 1 month after vaccination* in each vaccine group
 
	
 
Serotype-specific OPA titers
 

Secondary Safety	Secondary Safety	Secondary Safety
To describe the reactogenicity profile of PPSV23 following 13vPnC in Japanese participants (only for participants enrolled at Japan sites).	In participants receiving at least 1 dose of study intervention and having safety follow-up after vaccination from each vaccine group: 
 
The percentage of participants reporting prompted local reactions within 10 days after the second vaccination (PPSV23 or saline)
 
The percentage of participants reporting prompted systemic events within 7 days after the second vaccination (PPSV23 or saline)
 
	
 
Prompted local reactions (redness, swelling, and pain at the injection site)
 
Prompted systemic events (fever, headache, fatigue, muscle pain, and joint pain)
 

\* Note: "1 month after vaccination" refers to 1 month after vaccination with 20vPnC (20vPnC/saline group), or 1 month after vaccination with 13vPnC for the 13 matched serotypes or PPSV23 for the 7 additional serotypes (13vPnC/PPSV23 group).

## Overall Design

This Phase 3, multicenter, randomized, double-blind study will be conducted at investigator sites in Japan, Korea, and Taiwan.

Approximately 1400 participants 60 years of age and older at enrollment will be randomized into 2 groups in a 1:1 ratio by center-based randomization: 20vPnC/saline group and 13vPnC/PPSV23 group. Each participant will be randomized to receive either 20vPnC or 13vPnC (control vaccine) at Vaccination 1. Participants who received 20vPnC at Vaccination 1 in the 20vPnC/saline group will receive saline at Vaccination 2. Participants who received 13vPnC at Vaccination 1 in the 13vPnC/PPSV23 group will receive PPSV23 at Vaccination 2.

On Day 1 (Visit 1), participants will be assessed for eligibility, have blood drawn for immunogenicity assessments, and receive 20vPnC or 13vPnC administered by blinded site staff. Participants will be observed for at least 30 minutes after vaccination by blinded site staff, who will record AEs occurring during that time. Participants will also receive safety follow-up and e-diary instructions at the visit. Prompted systemic events (fever, headache, fatigue, muscle pain, and joint pain) occurring within 7 days after vaccination and prompted local reactions (redness, swelling, and pain at the injection site) occurring at the 20vPnC or 13vPnC injection site within 10 days after vaccination will be collected daily in the e-diary. Use of antipyretic/pain medications will be collected daily in an e-diary for 7 days after vaccination.

Participants will return for Visit 2 (28 to 42 days after Visit 1), and information will be collected from the participants on AEs, SAEs, and e-diary follow-up (as needed). Blood will be drawn for immunogenicity assessments. Saline will be administered to participants who previously received 20vPnC, and PPSV23 will be administered to participants who previously received 13vPnC, by a third-party unblinded site staff member. Participants will be observed for at least 30 minutes after vaccination by blinded site staff, who will record AEs occurring during that time. Participants will also be reminded about safety follow-up. The control participants are receiving a schedule that has been studied previously with no safety concerns, but it is a research schedule and a specific request has been made by the PMDA to collect additional information in the Japanese population. For participants enrolled at **Japan sites**, prompted local reactions occurring at the saline or PPSV23 injection site within 10 days after vaccination and prompted systemic events occurring within 7 days after vaccination will be collected daily in the e-diary. Use of antipyretic/pain medications will be collected daily in an e-diary for 7 days after vaccination.

Participants will return for Visit 3 (28 to 42 days after Visit 2) and information will be collected from the participants on AEs and SAEs. Blood will be drawn for immunogenicity assessments.

## Number of Participants

Approximately 1400 participants will be enrolled to achieve a target of 1260 evaluable participants (630 participants in each vaccine group) (assuming a 10% nonevaluable dropout rate). Approximately 700 participants will be enrolled from Japan, approximately 500 from Korea, and approximately 200 from Taiwan. The study will target enrolment of 50 %, or more, adults  $\geq 65$  years of age in each country. Note however, that the enrolment targets are approximations, and may not be achieved, particularly for the older age group. Randomization into the 2 vaccine groups will be managed within the age stratification (50 to 64 years of age and  $\geq 65$  years of age).

Note: "Enrolled" means a participant's agreement to participate in a clinical study following completion of the informed consent process. Potential participants who are screened for the purpose of determining eligibility for the study, but do not participate in the study, are not considered enrolled, unless otherwise specified by the protocol.

## Intervention Groups and Duration

Each participant will participate in the study for approximately 2 months. Based on an 8-month enrollment period, the study duration will be approximately 10 months.

Participants will receive either 20vPnC and saline or 13vPnC and PPSV23.

[figure not shown]
CCI

## Statistical Methods

The primary safety objective will be evaluated by descriptive summary statistics for local reactions, systemic events, AEs, and SAEs for each vaccine group. A 3-tier approach will be used to summarize AEs.

Primary immunogenicity objectives will be evaluated by formal hypothesis tests for NI of the immune responses to 20vPnC relative to immune responses to the control vaccine. NI for a serotype will be declared if the lower bound of the 2-sided CI for the serotype-specific OPA GMR of 20vPnC relative to control for that serotype is greater than 0.5 (2-fold criterion), with control being 13vPnC for the 13vPnC serotypes and PPSV23 for the 7 additional serotypes. CCI

Serotype-specific OPA GMTs, serotype-specific OPA GMFRs, percentages of participants with OPA titers  $\geq$  LLOQ, and  $\geq 4$ -fold rises in OPA titers, CCI will also be provided for each vaccine group.

Immunogenicity and safety results will also be descriptively summarized by country (Japan, Korea, and Taiwan).

## **1.2. Schema**

Not applicable.

### 1.3. Schedule of Activities

The SoA table provides an overview of the protocol visits and procedures. Refer to the STUDY ASSESSMENTS AND PROCEDURES section of the protocol for detailed information on each procedure and assessment required for compliance with the protocol.

The investigator may schedule visits (unplanned visits) in addition to those listed in the SoA table, in order to conduct evaluations or assessments required to protect the well-being of the participant.

Visit Number	1	2	3
Visit Description	Vaccination 1	Vaccination 2	Follow-up After Vaccination 2
Visit Type	Clinic Visit	Clinic Visit	Clinic Visit
Visit Window (Days)	Day 1	28 to 42 Days After Vaccination 1	28 to 42 Days After Vaccination 2
Obtain informed consent	X		
Assign participant number	X		
Record demography	X		
Conduct clinical assessment, including collecting medical history data and smoking history	X		
Record nonstudy vaccinations	X	X	X
Record concomitant medications used to treat SAEs	X	X	X
Measure height and weight	X		
Measure prevaccination oral temperature	X	X	
Contraception check, if applicable a	X	X	X
Review inclusion and exclusion criteria	X		
Review temporary delay criteria	X	X	X
Review continued eligibility		X	X
Assign randomization number	X		
Obtain blood sample for immunogenicity (~30 mL) b	X	X	X
Administer study intervention	X	X	
Observe and record acute reactions for at least 30 minutes after study intervention administration	X	X	
Provide a participant contact card	X		

Visit Number	1	2	3
Visit Description	Vaccination 1	Vaccination 2	Follow-up After Vaccination 2
Visit Type	Clinic Visit	Clinic Visit	Clinic Visit
Visit Window (Days)	Day 1	28 to 42 Days After Vaccination 1	28 to 42 Days After Vaccination 2
Provide participant with an e-diary (device or application), thermometer, and measuring device and instruct how to collect prompted local reactions, systemic events, and use of pain/antipyretic medications c	X		
Review e-diary d		X	X e
Collect e-diary (if device provided)		X f	X e
Record and report AEs and SAEs g	X-----		X

- a. The investigator or designee will inform male participants who are able to father children of the need to use highly effective contraception consistently and correctly until 28 days after the last dose of study intervention and document the conversation and the participant's affirmation in the participant's chart.
- b. Blood sample will be collected prior to vaccination at Visits 1 and 2.
- c. Participants will record in an e-diary prompted local reactions and systemic events occurring within 10 and 7 days, respectively, after Vaccination 1. Use of antipyretic/pain medications will also be prompted for and collected daily in an e-diary for 7 days after Vaccination 1. In addition, participants enrolled at Japan sites will record prompted local reactions and systemic events and use of antipyretic/pain medications in an e-diary after Vaccination 2 (collection periods will be the same as the collection periods after Vaccination 1). Participants will be instructed to contact the study staff or investigator if they experience redness or swelling measuring >20 measuring device units or severe pain at the injection site or any Grade 4 prompted systemic event.
- d. Designated site staff will review e-diary data online at frequent intervals (daily is optimal) for the 10 days following Vaccination 1 and Vaccination 2 (Japan sites only) to evaluate participant compliance and reported events as part of the ongoing safety review. Any e-diary devices given to participants are to be collected no later than Visit 2 and Visit 3 (Japan sites only).
- e. Only Japan sites.
- f. Korea and Taiwan sites.
- g. If the participant consents, participants withdrawn from the study will receive a 1-month safety follow-up after their last dose of study intervention for collection of any SAEs.

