## **7. DISCONTINUATION OF STUDY INTERVENTION AND PARTICIPANT DISCONTINUATION/WITHDRAWAL**

### **7.1. Discontinuation of Study Intervention**

Participant eligibility must be confirmed prior to each vaccination in order to continue in the study.

If a participant no longer meets the eligibility criteria during the vaccination period of the study, further vaccinations should be discontinued, but the participant may remain in the study. If a participant is discontinued from vaccination and the participant consents, safety follow-up will be conducted as per [Section 8.3](#) (AEs and SAEs will be collected for 1 month after the last study vaccination).

In rare instances, it may be necessary for a participant to permanently discontinue study intervention (definitive discontinuation). Reasons for definitive discontinuation of study intervention include the following: the participant no longer meets eligibility criteria, specific protocol deviations, withdrawals by the participant, and certain AEs or SAEs.

Note that discontinuation of study intervention does not represent withdrawal from the study. If study intervention is definitively discontinued, the participant will remain in the study to be evaluated for safety. See the SoA for data to be collected at the time of discontinuation of study intervention and follow-up for any further evaluations that need to be completed.

In the event of discontinuation of study intervention, it must be documented on the appropriate CRF/in the medical records whether the participant is discontinuing further receipt of study intervention or also from study procedures, postvaccination study follow-up, and/or future collection of additional information.

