### **8.3.1. Time Period and Frequency for Collecting AE and SAE Information**

The time period for actively eliciting and collecting AEs and SAEs (“active collection period”) for each participant begins from the time the participant provides informed consent, which is obtained before the participant’s participation in the study (ie, before undergoing any study-related procedure and/or receiving study intervention), through and including Visit 3.

Follow-up by the investigator continues throughout and after the active collection period and until the AE or SAE or its sequelae resolve or stabilize at a level acceptable to the investigator and Pfizer concurs with that assessment.

For participants who are screen failures, the active collection period ends when screen failure status is determined.

If the participant withdraws from the study and also withdraws consent for the collection of future information, the active collection period ends when consent is withdrawn.

If a participant definitively discontinues or temporarily discontinues study intervention because of an AE or SAE, the AE or SAE must be recorded on the CRF and the SAE reported using the Vaccine SAE Reporting Form.

Investigators are not obligated to actively seek AEs or SAEs after the participant has concluded study participation. However, if the investigator learns of any SAE, including a death, at any time after a participant has completed the study, and he/she considers the event to be reasonably related to the study intervention, the investigator must promptly report the SAE to Pfizer using the Vaccine SAE Reporting Form.

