6.1.1.3. Adverse Events

6.1.1.3.1. Main Analysis

- Estimand: The percentage of participants reporting AEs within 1 month after vaccination with 20vPnC or 13vPnC.

- Analysis set: Safety population ([Section 4](#)).
- Analysis time point: Within 1 month after vaccination.
- Analysis methodology: 3-Tiered approach as described in [Section 5.2.1](#).
- Intercurrent events and missing data: No missing values will be imputed except for partial AE start dates ([Section 5.3](#)).
- Reporting results: For all 3 tiers, the numerator (n) and the denominator (N) used in the percentage calculation, the percentage (%), and the corresponding 2-sided 95% Clopper-Pearson CI for participants reporting any AE, by each system organ class and each preferred term within system organ class, will be presented by vaccine group.

In addition, for AEs classified as Tier 2 events, the differences in percentages (20vPnC/saline - 13vPnC/PPSV) and associated 2-sided 95% CIs using the Miettinen and Nurminen method will be provided.

Further, for Tier 1 events, if any are identified, the difference in percentages, the associated 2-sided 95% CI for the risk difference, and the asymptotic p-values will also be provided.

If any nonserious AEs are reported to occur before vaccination at Visit 1, they will not be included in the summary but will be included in the AE listings.

CCI

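### SoA footnote g limits follow-up of withdrawn participants to SAEs, in conflict with Protocol 8.3.1, so the primary 1-month AE percentage can be slightly underestimated

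*Protocol*

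**What the plan says.** Footnote g in Protocol 1.3 is attached to the row for recording and reporting AEs and SAEs. If the participant consents, it provides that "participants withdrawn from the study will receive a 1-month safety follow-up after their last dose of study intervention for collection of any SAEs".

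Protocol 8.3.1 defines one active collection period for both kinds of event. It describes "The time period for actively eliciting and collecting AEs and SAEs" for each participant as running from informed consent "through and including Visit 3". It gives two early closures. One is for screen failures. The other is for a participant who withdraws from the study and "also withdraws consent for the collection of future information, the active collection period ends when consent is withdrawn".

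Protocol 7.1 has a parallel rule for a different group, those who stop vaccination but stay in the study: "AEs and SAEs will be collected for 1 month after the last study vaccination".

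Protocol 7.2 asks a withdrawing participant to return for a final visit, where applicable, with the next visit's procedures as far as the participant agrees. It also requires AEs ongoing at withdrawal to be followed up.

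The endpoint affected is a primary safety estimand, given in SAP 6.1.1.3.1 as "The percentage of participants reporting AEs within 1 month after vaccination with 20vPnC or 13vPnC". SAP Section 4 defines the safety population as everyone who received at least one dose. SAP 6.1.1.3.1 allows no imputation apart from partial AE start dates.

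**The concern.** Footnote g covers withdrawn participants who agree to be contacted. Those are the people for whom 8.3.1 leaves AE collection open, yet the footnote asks only about serious events. For a participant withdrawn before Visit 2, the last dose is Vaccination 1, so the footnote's 1-month contact covers the same window as the primary AE estimand. A site that follows the footnote makes the contact and has no instruction to ask about nonserious AEs.

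Such a participant stays in the SAP denominator, and an AE nobody asked about counts as no AE. The error runs one way: the AE percentage can only fall. What is at stake is the completeness of a primary safety percentage and the consistency of the protocol's rule for collecting it.

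**Working it through.** **Comparing the texts**

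| Participant | Footnote g | Section 8.3.1 |
|---|---|---|
| Withdraws, consents to contact | SAEs only, 1 month after last dose | AEs and SAEs through Visit 3 |
| Withdraws, also withdraws consent for future information | No follow-up | Collection ends |

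The rules differ in the first row only.

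**Which nonserious AEs can be lost from the primary estimand**

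1. AEs before withdrawal are recorded in any case.
2. Visit 2 takes place 28 to 42 days after Visit 1 and asks about AEs since Visit 1 (Protocol 8.11.2). Participants withdrawn at or after Visit 2 lose essentially nothing.
3. A participant withdrawn before Visit 2 who attends the 7.2 final visit is asked about AEs up to that visit.
4. The any-AE percentage counts participants, so someone with an AE already recorded is not lost from it.

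What remains is a first nonserious AE, after withdrawal and after any final visit, within 1 month of Vaccination 1, in a consenting participant withdrawn before Visit 2 whose site follows footnote g.

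**Size**

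The only related figure in the plan is the enrolment inflation in Protocol 9.2: 630 / (1 − 0.10) = 700 per group, which reproduces. The plan states no pre-Visit 2 withdrawal rate and no expected AE rate.

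Let w be the share of a group withdrawn between Vaccination 1 and Visit 2, and q the probability that such a person's only AE in the window goes unrecorded as described. Both are assumptions.

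Shortfall in the AE percentage = w × q; participants missed = 700 × w × q.

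| w | q | Participants missed per group | Percentage points |
|---|---|---|---|
| 0.5% | 5% | 0.18 | 0.025 |
| 1% | 10% | 0.7 | 0.1 |
| 3% | 10% | 2.1 | 0.3 |
| 5% | 10% | 3.5 | 0.5 |
| 5% | 20% | 7.0 | 1.0 |

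Another way to reach q is to assume that half the window remains at withdrawal and that the monthly AE rate is 10% to 30%. Then q = 0.5 × 10% to 0.5 × 30%, or 5% to 15%. With w from 1% to 5% (7 to 35 of 700), this gives 0.35 to 5.25 participants, or 0.05 to 0.75 points. These values run high, because they make no allowance for attendance at the final visit or for AEs already recorded.

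For scale, an assumed AE rate of 10% (70 of 700) has a Clopper-Pearson 95% CI of 7.9% to 12.5%.

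**The case against.** The strongest defence is that the passages can be read together. Section 8.3.1 also says: "Investigators are not obligated to actively seek AEs or SAEs after the participant has concluded study participation". If withdrawal concludes participation, footnote g is an extra SAE contact and not a restriction. The text never says that withdrawal is conclusion, however. If it were, the separate rule that collection ends when consent is also withdrawn would be redundant. Footnote g itself continues active follow-up after withdrawal. The conflict stands.

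A second defence is that Section 1.3 calls the SoA an overview and refers to the assessments section, which contains 8.3.1. Against that, 7.2 sends sites to the SoA at discontinuation, and Section 8 makes adherence to it a requirement. Precedence is unclear, which is a reason to align the two texts. It does not prove that sites would skip nonserious AEs.

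A third defence is the 7.2 final visit, and much of it stands: where attended, that visit narrows the gap. But it is requested only where applicable, has no fixed date, and can be missed without a protocol deviation, so it does not close the gap.

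A reader might also infer that 7.1 contradicts footnote g. It does not, since 7.1 covers participants who stop vaccination but remain in the study.

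**Conclusion.** The inconsistency between footnote g and 8.3.1 is real and should be reconciled. Its effect on the primary AE percentage is one-directional, conditional on sites following the footnote, and probably well under 1 percentage point per group. The 1.0-point figure needs both assumed inputs at the top of their ranges. The endpoint is descriptive, and no hypothesis test or sample size depends on it.

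Four stronger readings are tempting, and the documents do not support them:

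- *The primary percentage misses all nonserious AEs of withdrawn participants.* Events before withdrawal, at Visit 2 or at a final visit are collected.
- *10% of each group is affected.* Protocol 4.1.2 gives 10% as a nonevaluable rate. Under 9.3, evaluability also fails for out-of-window blood draws, absence of a valid titer or major deviations. Putting all 10% before Visit 2 would give 0.5 to 2.0 points for q of 5% to 20%, but nothing in the plan suggests that.
- *Preferred terms would drop out of Tier 2.* The few missed participants would be spread over all terms. A term in Tier 3 still has its count, percentage and Clopper-Pearson CI reported (SAP 6.1.1.3.1).
- *The between-group comparison is biased.* That needs withdrawal or unrecorded AEs to differ by arm. The documents give no basis for this, and both arms receive a blinded conjugate vaccine at Vaccination 1.

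**What to change.** In SoA footnote g, state that the 1-month follow-up is for collection of any AEs and SAEs, not SAEs alone, so that it agrees with 8.3.1. The contact is already planned and already depends on consent, so no visit, contact or staff is added. The cost is a one-line protocol correction and a slightly longer call.

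No SAP change is needed. The disposition summary in SAP 6.5.2.1 already counts participants vaccinated at Visit 1 and at Visit 2. The difference gives an upper bound on w, so the report can replace the assumed range with an observed one.
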